2 INTRODUCTION

2.1 Study Rationale

An in vitro cytochrome P450 (CYP) identification study suggested that ASP8062 is mainly metabolized by CYP3A4, while morphine shows no inhibitory effect on CYP3A in an in vitro study [Haaz et al, 1998]. Morphine is metabolized by multiple UDP-glucuronosyltransferases [De Gregori et al, 2012; Sato et al, 2012; Court et al, 2003; Projean et al, 2003]. Therefore, the pharmacokinetic drug-drug interaction (DDI) potential of ASP8062 with opioids is considered to be low. Potential interaction such as opioid effects on respiratory depression is theoretically possible because both ASP8062 and opioids are centrally active [Pattinson, 2008].

For future studies in opioid use disorder (OUD) patients, ASP8062 will be coadministered with opioids, including standard medication-assisted treatments such as buprenorphine/naloxone. Among opioid receptors, the μ -receptor is considered to play a role in the decrease in the respiratory response to hypoxia, resulting in a decreased stimulus to breathe and the development of apnea [Schiller & Mechanic, 2019]. ASP8062 has not been observed to directly interact with opioid receptor [study 8062-PH-9005] and the preclinical DDI study [study 8062-PH-9055] between ASP8062 and morphine, a full agonist for opioid μ -receptor, failed to find any pharmacodynamic (i.e., respiratory depression) interaction including general condition. This clinical DDI/safety study will provide relevant safety (particularly for respiratory depression), tolerability and pharmacokinetic data in order to assess the potential risk of ASP8062 coadministered with morphine, a full agonist for opioid μ -receptor to support future studies in this patient population. The study was designed particularly to investigate if ASP8062 has any additive effect on top of morphine by instituting the sensitive measure of end tidal carbon dioxide (CO_2), using a single morphine dose slightly above the highest approved individual morphine dose, but presumably still allowing room to detect potential additive effects of ASP8062.

2.2 Background

ASP8062 is a novel compound with positive allosteric modulator (PAM) activity on the gamma-aminobutyric acid type B (GABA_B) receptor that is intended for oral administration and is currently being developed for the treatment of OUD and alcohol use disorder.

ASP8062 is a crystal, which is practically insoluble in water and slightly soluble in ethanol.

An estimated 2.1 million Americans had an OUD in 2017 [Substance Abuse and Mental Health Services Administration, 2018]. Overdose deaths due to opioid use have skyrocketed to over 47600 in 2017 [Scholl et al, 2018]. National Institute on Drug Abuse (NIDA) data show that use of opioids can lead to neonatal abstinence syndrome [NIDA, 2019a] as well as the spread of infectious diseases like human immunodeficiency virus (HIV) and hepatitis [NIDA, 2019b]. Medication assisted treatment with buprenorphine (with or without naloxone), methadone or naltrexone is the current standard of care, and has resulted in decreases in opioid use, overdose deaths, criminal activity and infectious disease transmission [Mattick et al, 2014; Schwartz et al, 2013; Mattick et al, 2009]. However, buprenorphine can

induce withdrawal on first administration, has an overdose potential, induces withdrawal symptoms and a loss of tolerance on cessation, is also subject to abuse and diversion and can cause respiratory suppression. Buprenorphine's ceiling effect may limit its effectiveness in patients with ongoing opioid use [Bart, 2012].

The Diagnostic and Statistical Manual of Mental Disorders, edition 5 (DSM-5) defines substance use disorders as a constellation of recurrent pathological cognitive, behavioral and physiological symptoms arising from the ongoing use of a substance. The DSM-5 has combined the Diagnostic and Statistical Manual of Mental Disorders, edition 4 categories of substance abuse and substance dependence under the single heading of substance use disorders, which is classified by severity based on the number of symptom criteria (out of a total of 11) that are met: mild (2 to 3 criteria), moderate (4 to 5 criteria) and severe (more than 6 criteria) [Hasin et al, 2013]. Different drugs produce different effects on the user, but important shared features include a dysregulation of brain reward pathways and an overactive brain stress system, which together reinforce use of the substance to achieve a pleasurable high, even if pursuing this high incurs great cost or negative consequences for the user.

Gamma-aminobutyric acid (GABA), the most abundant inhibitory neurotransmitter, activates 2 types of receptors: ionotropic GABA type A receptors [Olsen & Sieghart, 2008] and metabotropic GABA_B receptors [Bowery et al, 2002]. Studies with GABAergic drugs and drugs of abuse have indicated that the GABA_B receptor mediates suppression of self-administration/craving across several drug modalities. Drugs triggering abuse act by enhancing dopamine release in the ventral tegmental, striatal, and prefrontal cortical areas of the brain. The effects of GABAergic compounds on decreasing drug self-administration and drug-seeking behavior act by either directly or indirectly decreasing dopamine release in the aforementioned brain areas [Filip et al, 2015].

GABA_B agonists or PAMs have been found to attenuate opioid-, alcohol-, cocaine- and nicotine-seeking behavior [Augier et al, 2017; Vlachou et al, 2011; Franklin et al, 2009; Filip & Frankowska, 2007; Paterson et al, 2004; Di Ciano & Everitt, 2003b; Di Ciano & Everitt, 2003a] and also attenuate the drugs of abuse-evoked changes during intracranial self-stimulation [Vlachou et al, 2011; Paterson et al, 2008; Slattery et al, 2005]. However, activation of GABA_B receptors by orthosteric agonists such as baclofen induces side effects such as sedation, somnolence, excessive weakness, vertigo and cognitive impairment. The sedative properties of baclofen limits its potential widespread therapeutic utility [Dario & Tomei, 2004]. Accordingly, activation of GABA_B receptors by PAMs is one of the prioritized medication treatment approaches for NIDA in response to the opioid crisis [Rasmussen et al, 2019].

For information on the nonclinical and clinical data of ASP8062, please refer to the [Investigator's Brochure].

2.3 Risk/Benefit Assessment

2.3.1 Risk Assessment

ASP8062 has a potential to decrease use of illicit opioid drugs and improve the quality of life in patients with OUD. In the present study however where only a single daily 25 mg oral dose of ASP8062 will be administered for 10 consecutive days, there is no likelihood of a therapeutic effect. Given the safety profile of ASP8062 when administered to healthy participants, there appears to be relatively minimal risk to participants taking a daily 25 mg oral dose. The clinical unit has appropriately trained staff and required equipment available to treat participants presenting with both opioid withdrawal and morphine associated adverse events (AEs) including respiratory depression.

The risks of morphine immediate-release tablets are well known. Risks are mitigated in that only a single dose of morphine will be administered on day 10 following 10 consecutive daily administrations of ASP8062 [Morphine Sulfate Package Insert]. Risks are also minimized because the participants are confined at a clinical unit that has administered a range of opioids, including morphine. Side effects of opioids in general include respiratory depression, central nervous system depression and drowsiness, euphoria, feelings of relaxation, dependence, reduction of gastrointestinal motility, hepatitis with or without jaundice, allergic reactions, impairment in the ability to drive, orthostatic hypotension, elevation of cerebrospinal fluid pressure and intracholendochal pressure.

There is no expected benefit to the participants from the administration of morphine.

This will be the first study where a multiple daily oral dose of ASP8062 is administered in participants that will also be given morphine after the participants have reached near steady-state peak to trough exposures of ASP8062. Risks are minimized by confining participants in an experienced clinical unit testing the effects of approved medications or new chemical entities when combined with morphine. This study is also being conducted after the initiation of the phase 1b study examining a single dose of ASP8062 (60 mg) in participants also administered buprenorphine-naloxone at doses/exposures consistent with OUD standard of care. Continuous pulse oximetry and capnography for at least 8 hours will be employed on day 10 when ASP8062 is given with morphine so that the potential for respiratory depression will be noted immediately, and appropriate medical treatment may be given. Participants will also be monitored by experienced staff for signs of opioid withdrawal. Vital signs will be monitored daily from days 9 to 16 and electrocardiograms (ECGs) will be monitored on day 10 to detect potential cardiovascular symptoms several hours postdose. AEs will be assessed daily throughout the study. Potential hepatic toxicity will be monitored with clinical laboratory testing on at least a daily basis from days 10 to 16 of the investigational period.

2.3.2 Benefit Assessment

There is not expected to be a benefit from multiple consecutive daily oral doses of ASP8062 for 10 days in addition to a single oral dose of 45 mg morphine immediate-release tablets.

2.3.3 Overall Risk-Benefit Conclusion

Participants in this study will not benefit from administration of ASP8062. In contrast, participants might experience AEs related to ASP8062 or procedural complications (e.g., blood draws, slight skin irritation from the adhesive on the ECG electrodes).

Overall, the risk associated with the participation of recreational opioid using participants in this study is considered acceptable.

3 OBJECTIVES, ENDPOINTS AND ESTIMANDS

Table 3 Study Objectives and Endpoints

Objectives	Endpoints
Primary	
• To assess the safety and tolerability of multiple doses of ASP8062 or placebo alone and in combination with a single dose of morphine• Nature, frequency and severity of AEs• Clinical laboratory tests (hematology, biochemistry and urinalysis)• Vital signs (blood pressure, pulse and respiratory rate)• 12-lead ECG• C-SSRS• SpO₂• End tidal CO₂
Secondary	
• To assess the potential for pharmacokinetic interaction between ASP8062 and morphine• Plasma ASP8062: AUC₂₄ and C_{max}• Plasma morphine and its metabolites (M3G and M6G): AUC_{inf}, AUC_{last} and C_{max}
Exploratory	
• To assess additional safety and tolerability of multiple doses of ASP8062 or placebo alone and in combination with a single dose of morphine• Oral temperature• ARCI-49• To assess the general pharmacokinetic parameters of ASP8062, its metabolites, morphine and its metabolites• Plasma ASP8062: CL/F, t_{1/2}, t_{max}, t_{lag}, V_z/F, C_{trough} and PTR• Plasma ASP8062 metabolites (AS3486189, AS3486191 and AS3486192): C_{max}, AUC₂₄, t_{1/2}, t_{max}, t_{lag}, V_z/F, C_{trough} and PTR• Plasma morphine and its metabolites (M3G and M6G): AUC_{inf}(%extrap), CL/F (morphine), t_{1/2}, t_{max}, t_{lag} and V_z/F• Plasma ASP8062 metabolites (AS3486189, AS3486191 and AS3486192): AUC₂₄ and C_{max}

AE: adverse event; ARCI-49: 49-item short form of Addiction Research Center Inventory scale; CO₂: carbon dioxide; C-SSRS: Columbia-suicide severity rating scale; ECG: electrocardiogram; M3G: morphine-3β-D-glucuronide; M6G: morphine-6β-D-glucuronide; SpO₂: blood oxygen saturation

Estimands

Not applicable.

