4 STUDY DESIGN AND DOSE RATIONALE

4.1 Overall Study Design

This will be a randomized, participant- and investigator-blinded, placebo-controlled, single sequence study comprising of male and female recreational opioid-using participants.

Approximately 24 male and female participants will be randomly assigned to complete at least 18 participants. An attempt will be made to enroll 1 female participant for every 3 male participants. The study will be conducted at 1 study site in the US.

Participants will be screened for up to 28 days prior to first investigational product (IP) administration. Eligible participants will be admitted to the clinical unit on day -1 and will be residential for a single period of 17 days/16 nights. After randomization, participants will receive multiple oral doses of ASP8062 or placebo (2:1 ratio) on days 1 through 10. On day 10, all participants will also receive a single oral dose of morphine immediately after the ASP8062 or placebo dose followed by a 144-hour in-house blood sampling period.

Scheduled safety and tolerability assessments will be conducted as indicated in the Schedule of Assessments [Table 1]. Participants are to remain awake, seated or semirecumbent and avoid lying on either the left or right side for at least 4 hours postdose on days 9 and 10.

Participants will be discharged from the clinical unit on day 16 on the condition that all required assessments have been performed and that there are no medical reasons for a longer stay in the clinical unit.

The study will be completed with an end-of-study visit (ESV). The ESV will take place 5 to 9 days after the day 16 pharmacokinetic sample is collected or at early discontinuation/termination from the study.

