9.4.4.2 Estimation of Pharmacokinetic Parameters

Noncompartmental analysis will be used for the calculation of plasma pharmacokinetic parameters using Phoenix version 6.3 or higher (Certara LP, 100 Overlook Center, Suite 101, Princeton, NJ 08540, US).

Plasma pharmacokinetic parameters of morphine and its metabolites (M3G and M6G) in combination with placebo and in combination with ASP8062 will be listed and summarized using descriptive statistics.

Plasma pharmacokinetic parameters of ASP8062 and its metabolites (including AS3486189, AS3486191 and AS3486192) alone and ASP8062 in combination with morphine will be listed and summarized using descriptive statistics.

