SAE	serious adverse event
SAF	safety analysis set
SMQ	Standardized MedDRA Queries
SOP	standard operating procedure
SpO ₂	blood oxygen saturation
SUSAR	suspected unexpected serious adverse reactions
t _½	terminal elimination half-life
TBL	total bilirubin
TEAE	treatment-emergent adverse event
t _{lag}	time prior to the time corresponding to the first measurable (nonzero) concentration
t _{max}	time of maximum concentration
ULN	upper limit of normal
USM	urgent safety measure
V _z /F	apparent volume of distribution during terminal phase after oral/extravascular administration
WOCBP	woman of childbearing potential

Definition of Key Study Terms

Terms	Definition of Terms
Baseline	Assessments of participants as they enter a study before they receive any treatment.
Endpoint	Variable that pertains to the efficacy or safety evaluations of a study. Note: not all endpoints are themselves assessments since certain endpoints might apply to populations or emerge from analysis of results. That is, endpoints might be facts about assessments (e.g., prolongation of survival).
Enroll	To register or enter a participant into a study. Note: once a participant has received the IP or placebo, the protocol applies to the participant.
Investigational period	Period of time where major interests of protocol objectives are observed and where the test product or comparative drug (sometimes without randomization) is given to a participant and continues until the last assessment after completing administration of the test product or comparative drug.
Investigational product	The drug, device, therapy or process under investigation in a study that is believed to have an effect on outcomes of interest in a study (e.g., health-related quality of life, efficacy, safety and pharmacoeconomics).
Randomization	The process of assigning participants to treatment or control groups using an element of chance to determine assignments in order to reduce bias. Note: unequal randomization is used to allocate participants into groups at a differential rate; for example, 3 participants may be assigned to a treatment group for every 1 assigned to the control group.
Screen failure	Potential participant who signed the ICF, but did not meet one or more criteria required for participation in the study and was not randomized.
Screening	A process of active consideration of potential participants for randomization in a study.

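### Vz/F is listed for five metabolites that are never dosed, so the reported value would not be their volume of distribution and, for M3G and M6G, could shift with formation alone

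*Combined protocol and SAP*

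**What the plan says.** Section 3, Table 3, repeated in the Section 1.1 synopsis, sets out the exploratory pharmacokinetic parameters line by line.

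- ASP8062 metabolites (AS3486189, AS3486191 and AS3486192): "C_{max}, AUC₂₄, t_{1/2}, t_{max}, t_{lag}, V_z/F, C_{trough} and PTR". CL/F is absent; Vz/F is present.
- Morphine line: "Plasma morphine and its metabolites (M3G and M6G): AUC_{inf}(%extrap), CL/F (morphine), t_{1/2}, t_{max}, t_{lag} and V_z/F". CL/F carries a restriction to the parent; Vz/F, in the same line, carries none, so as written it also covers M3G and M6G.

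The compounds administered are ASP8062 or placebo on days 1 to 10 and, on day 10, morphine: "all participants will also receive a single oral dose of morphine immediately after the ASP8062 or placebo dose" (Section 4.1). No metabolite is dosed.

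Section 10.11 defines Vz/F as "apparent volume of distribution during terminal phase after oral/extravascular administration". Section 9.4.4.2 says "Noncompartmental analysis will be used for the calculation of plasma pharmacokinetic parameters" and gives no separate formula for metabolites and no correction for the fraction of dose converted. The same section says that "Plasma pharmacokinetic parameters of morphine and its metabolites (M3G and M6G) in combination with placebo and in combination with ASP8062" will be listed and summarised descriptively.

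**The concern.** CL/F and Vz/F both need an administered dose of the compound being measured. A metabolite has none, and the only dose available to a noncompartmental calculation is that of the parent. The result is then labelled as an apparent volume although it also depends on how much parent was converted. Table 3 already separates parent from metabolite for clearance, but not for volume.

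The secondary objective is pharmacokinetic interaction between ASP8062 and morphine, and Section 2.1 says morphine is metabolised by UDP-glucuronosyltransferases, the route to M3G and M6G. Section 9.4.4.2 summarises M3G and M6G with placebo and with ASP8062. A change in formation, which is one form the interaction could take, could thus be tabulated partly as a change in distribution.

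**Working it through.** The plan gives no figure for this parameter, so there is nothing to reproduce. The check is algebraic, with assumed ranges where the documents are silent.

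**Inputs from the documents.** The compounds dosed (Section 4.1), the analytes given Vz/F (Table 3), noncompartmental estimation (Section 9.4.4.2) and the route by which the glucuronides arise (Section 2.1).

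**Assumptions not in the documents.** The parent dose is used in the calculation. Glucuronidation accounts for a share g = 0.50 to 0.80 of morphine clearance. Any inhibition x is 20% to 50% and acts equally on M3G and M6G formation. The true metabolite volume and clearance stay fixed. First-pass formation is not modelled.

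**Step 1: what the reported value is.** The standard noncompartmental formula is Vz/F = Dose / (lambda_z × AUC). For a metabolite, AUC_m = fm × Dose / CL_m, where fm is the fraction of the dose reaching plasma as that metabolite. Substituting:

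reported Vz/F = CL_m / (fm × lambda_z)

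- Metabolite elimination rate-limiting: lambda_z = CL_m / V_m, so the value is V_m / fm.
- Formation rate-limiting: lambda_z is the parent's rate, CL_parent / V_parent. With fm = CL_formation / CL_parent, the value is CL_m × V_parent / CL_formation, which contains no V_m.

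Neither is the metabolite's own volume. In the elimination-limited case the value exceeds V_m by a factor 1/fm. For an assumed fm of 0.5 that is 1/0.5 = 2-fold, and for 0.05 it is 1/0.05 = 20-fold. In the formation-limited case the excess is larger. A molecular-weight factor would add a further constant but cancels in a ratio between groups.

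**Step 2: if the fraction formed itself falls.** With half-life unchanged, a 25% fall in fm gives 1/0.75 = 1.33, and a 50% fall gives 1/0.50 = 2.00.

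**Step 3: if the enzyme is inhibited by x.** Inhibition lowers formation clearance to (1 − x) of its value, but it also lowers total morphine clearance to (1 − g·x), so fm changes by (1 − x)/(1 − g·x).

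- Elimination-limited: ratio of reported Vz/F = (1 − g·x)/(1 − x).
- Formation-limited: ratio = 1/(1 − x), whatever g is.

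| Inhibition x | Elim.-limited, g = 0.50 | g = 0.65 | g = 0.80 | Formation-limited |
|---|---|---|---|---|
| 20% | 1.13 | 1.09 | 1.05 | 1.25 |
| 30% | 1.21 | 1.15 | 1.09 | 1.43 |
| 50% | 1.50 | 1.35 | 1.20 | 2.00 |

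Worked corners: (1 − 0.80 × 0.20)/0.80 = 0.84/0.80 = 1.05, and (1 − 0.50 × 0.50)/0.50 = 0.75/0.50 = 1.50. As g approaches 1, the elimination-limited ratio approaches (1 − x)/(1 − x) = 1, meaning no shift.

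A numerical one-compartment parent-metabolite model with first-order absorption and fixed metabolite volume agrees with these closed forms within 1%.

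**The case against.** The strongest reply is that little depends on this number. Vz/F is exploratory and only summarised. The ANOVA in Section 9.4.4.3 names AUC24 and Cmax, with a similar analysis for morphine and its metabolites, and does not name Vz/F. M3G and M6G AUCinf, AUClast and Cmax are secondary endpoints, and half-life is listed too. Because the value is dose over (lambda_z × AUC), any formation effect that moves it must also show in AUC or half-life. For example, at g = 0.50 and x = 50% in the formation-limited case, AUC falls to 0.667 and lambda_z to 0.750 of baseline, and 1/(0.667 × 0.750) gives the doubling. Section 2.1 also rates the interaction potential as low. All of this stands and limits the importance of the point.

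It is also fair that the Section 10.11 definition says apparent, and does not say that the analyte must be the compound administered; even for dosed morphine, an unknown F is in the denominator. That F is a property of the dosed compound, however, whereas the metabolite value also carries the fraction formed and may contain no metabolite volume.

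A reader might infer that any ASP8062 effect on glucuronidation would necessarily appear as a false change in M3G and M6G distribution, by a third or by twofold. The documents do not support that. Those figures belong to a fall in the fraction formed, not to enzyme inhibition. With half-life unchanged and g of 0.5 to 0.8, 25% inhibition gives 0.80/0.75 to 0.875/0.75, about +7% to +17%, and 50% gives +20% to +50%. The documents give neither g nor the rate-limiting step. Nor do they say why the restriction was put on CL/F alone, so calling it an oversight would be a guess.

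**Conclusion.** The point holds as a specification matter of low weight. As written, the plan yields Vz/F for five analytes that are never administered, and none of the five values would be that analyte's volume of distribution. This part needs no assumption beyond use of the parent dose.

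The consequence for the interaction question is conditional. An effect on glucuronidation could contribute to an apparent rise in M3G and M6G Vz/F with distribution unchanged. Under the assumptions in the working, the rise is about 5% to 50% if elimination-limited, 25% to 100% if formation-limited, and close to nil if elimination-limited with glucuronidation nearly the only route. No sample size, primary or secondary endpoint, or formal comparison is affected.

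**What to change.** In Table 3 and the Section 1.1 synopsis, write *CL/F and Vz/F (morphine)* in the line for morphine and its metabolites, and delete Vz/F from the line for AS3486189, AS3486191 and AS3486192. This matches the treatment of CL/F. Vz/F for ASP8062 itself stays.

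If the sponsor prefers to keep the metabolite values, a footnote should state that they are calculated from the parent dose, are uncorrected for the fraction formed, and are not to be read as volumes.

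The cost is a wording change in two places and one fewer parameter for five analytes. Sampling, assays and the planned comparisons are unchanged, and M3G and M6G exposure and half-life remain available for judging an effect on formation.
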